Email: [contact]

1. Summary of Changes to Standard Operating Procedure

February 3, 2016 ([name])

Various items that required clarification arose after the first few weeks of the study. The following clarifications were agreed upon:

- **Damage Control:** Allowed (definitive treatment done within 2 weeks after first operation)
- **Exfix Pin-Care:** 2 weeks with dressing and BID pin wash with alcohol. Check at 2 week follow up. If dry, remove dressing. If discharge present, continue with dressing and additional evaluations before 6 weeks
- **Exfix Treatment:** 3 months then the following at surgeon's discretion to be documented in eval form (1) removal, (2) removal with cast, (3) delayed exfix removal, or (4) other. Delayed exfix removal or other will be submitted for adjudication review
- **Antibiotics:** 3 options at surgeon's discretion with (1) CTX, (2) CTX + gentamycin, (3) CTX + gentamycin + metronidazole
- **Weight Bearing Protocol (all patients):** 6 weeks toe touch then at surgeon's discretion
- **Nurses:** 2 per week (number of patients will increase next Saturday)
- **# IM Nail Interlocks:** 4 total on all nailed patients (2 prox, 2 distal)
- **Continue with study without interruption:** Yes
- **Cohort Study:** Will now include non-primarily closeable patients (we will attempt to contact the patients who came in since the start of the study)

There was also a patient "borderline" fracture who will be included and followed-up. We have made a note and can exclude during data analysis if necessary.

February 13, 2016 ([name])

Following the presentation of an open tibia patient approximately 3 days after their injury, a discussion occurred regarding whether or not an upper limit would be set for patients in the cohort study who present >24 hours post-injury.

- ➔ It was decided that there would be no upper limit.

April 6, 2016 ([name])

- ➔ It was decided that exfix patients who receive a cast will have the cast paid for by the study since it is a complication of their randomization (and not part of their typical treatment plan)
- ➔ [name] will send out a revised budget

April 10, 206 ([name])

[name] noticed during his site visit to MOI that there was underreporting of pin tract infections in the external fixation group. Previously, the question, "are the schanz pin tracts infected?" would only

appear if a surgical site infection was identified and reported under the question, “does the patient have any wound problems?” The underreporting may have been due to ambiguity in this question and the responses that were available.

In the scheme of things, this does not have too bad of an effect on the data because it was only for the first 40 patients. Some of these had wound infections so they saw the question and others might not have had pin tract infection. Thus we only missed those who did not have a wound infection but did have a pin tract infection in exfix group in first 3 months of the study.

- ➔ It was decided that the question “are the schanz pin tracts infected?” would appear for all external fixation patients regardless of the response to the question “does the patient have any wound problems?” Due to the difficulty of tracking at what time point patients get their external fixators removed, this question will appear at all follow-up visits even after the external fixator may have been removed. An option “N/A – the external fixator has already been removed” is provided in this situation.

April 13, 2016

- ➔ [name] stated that study related travel for [name] (beyond his allotted Doris Duke funding) and others would be compensated under the study budget. [name] will revise the budget accordingly.

April 22, 2016

In order to streamline where complications are recorded, the following recommendations were made by [name] and [name]:

- ➔ Infections and wound complications will be moved to the “Complications and Review Form”
- ➔ If a complication was previously recorded for a patient, a prompt will appear on subsequent follow-up forms asking the team to review the complications form and make any necessary updates

2. Background & Significance

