2.3 Preliminary Data

Our Tanzanian colleagues conducted a preliminary study with similar research design over 12 months from March 2013 to February 2014. Fifty-four patients with Gustilo and Anderson Type 3A tibial shaft fractures were enrolled and randomly allocated to two treatment groups. Twenty six were treated with definitive external fixation, and 28 were managed with intramedullary nailing. Two patients were lost to follow-up from each group, leaving a total study population of 50 patients followed for 4.5 months.

As previously stated, the most common mechanisms of injury included motorcycle collisions (75.8%) and motor vehicle collisions (20.4%), followed by bicycle accidents and falls from height (combined 3.8%). Young men were most commonly affected. More than 60% of patients were treated within 16 hours from injury and 98% were treated within 24 hours from time of injury. Patients were treated according to standard open fracture protocols and randomized to two treatment groups undergoing either intramedullary nailing or external fixation.

We found no statistically significant difference in the rates of wound healing or incidence of deep infection (7.7% for IMN vs 12.5% for ex-fix). Twelve patients (46.2%) treated with external fixators developed superficial infection, none of which required implant removal. We observed a significantly faster time to callus formation in the intramedullary nail group (average 8.15 +/- 2.5 weeks, 92% at 10 weeks) when compared with the external fixation group (14.7 +/- 3.3 weeks, 25% at 10 weeks). Patients treated with intramedullary nails attained full weight bearing earlier than pts treated with external fixators. Malunion rates were also significantly lower in the intramedullary nail group, as two ex-fix patients (8.3%) were found to have significant post-operative limb length discrepancies and three (12.5%) were revised for angular or rotational malalignment, versus no malunions noted in the intramedullary nail group.

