4.1 Outcomes

The primary outcome for our study will be composite, all-cause reoperation within one year of definitive skeletal stabilization, excluding bedside irrigation and debridement for superficial pin tract infections or planned ex-fix removal. The use of composite outcomes has been validated in a wide range of clinical trials.¹⁹ Primary events included in our composite outcome are detailed in the following table.

A participant who undergoes conversion from ex-fix to nail within six weeks of surgery will be analyzed according to the initial treatment that was assigned by randomization. Patients who undergo conversion from ex-fix to nail more than six weeks after the index procedure will be considered to have undergone a reoperation and will therefore count toward the primary outcome. Conversion from nail to ex-fix, regardless of time point, will be considered a primary outcome event.

Primary Events

Infection or hematoma	Repeat incision and debridement or drainage for superficial or deep infection or hematoma following initial wound healing.
Bone grafting	Bone grafting for patients > 6 months from index surgery. Bone grafting will be considered after 6 months in the case of delayed radiographic healing with > 2 months pain on attempted weight bearing.
Implant conversion (e.g. Ex Fix to IM nail) or implant exchange (e.g. exchange nailing)	Implant conversion or implant exchange > 6 months from index surgery to facilitate union.
Implant removal	
 1) For construct failure with appropriate clinical indication (broken hardware, half-pin failure at bone/pin interface). 2) Intramedullary nail removal to facilitate union. 3) Intramedullary nail removal due to patient reported pain or local irritation
Dynamization of intramedullary nail	
To facilitate healing > 6 months from index surgery.
 
* Note: Auto-dynamization without clinical indication for removal of broken component will not be counted as a primary event.

Osteotomy	To correct malalignment
Amputation	For limb salvage failure

Secondary clinical outcomes will include:

1. Post-operative compartment syndrome.
2. Superficial infection, as defined by CDC surveillance definitions, to include pin tract infections and cellulitis which resolves with use of antibiotics and local wound care.
3. Deep infection, as defined by CDC surveillance definitions, to include deep abscess or osteomyelitis.

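### The early gap in pin-tract infection data is written off and the form repaired only prospectively, leaving superficial infection under-ascertained in the external-fixation arm alone

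*Protocol*

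**What the plan says.** The relevant text is the April 10 entry of Section 1 of the protocol (the year is misprinted but is evidently 2016). It records that "there was underreporting of pin tract infections in the external fixation group". The cause was form logic: the pin-tract question would only "appear if a surgical site infection was identified and reported under the question" on wound problems. The entry adds that this question and its response options may have been ambiguous.

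It then judges the consequence: "this does not have too bad of an effect on the data because it was only for the first 40 patients". It says who was lost: "we only missed those who did not have a wound infection but did have a pin tract infection in exfix group in first 3 months". The action is that the question "would appear for all external fixation patients regardless of the response to the question" on wound problems, at every follow-up visit, with an option for a fixator already removed. Nothing is said about visits already held.

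Section 4.1 lists superficial infection as a secondary clinical outcome, defined "to include pin tract infections and cellulitis which resolves with use of antibiotics and local wound care". Aim 2 in Section 3 compares its rate between arms. Section 6.5 shows the current question: it asks whether the pin tracts are infected now, with the answers yes, no, or not applicable because the fixator is off.

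**The concern.** Only external-fixation patients can have a pin-tract infection and only they are asked about it. Any loss therefore falls on one arm and flatters it in a planned between-arm comparison.

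The prospective repair does not close the gap. A patient whose pin tract was infected at an early visit and had healed by the next would correctly be answered no, or not applicable, at every later visit. The outcome definition nevertheless counts infections that settle with antibiotics and local care. The April 22 prompt to update the complications form does not help either, because it appears only when a complication is already on record.

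The early patients thus differ from the later ones in how infection was looked for, and the document fixes the view that this hardly matters.

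**Working it through.** **Timing.** Screening began on 14 December 2015 (Section 5.1). To 10 April 2016 is 118 days. The REDCap event schedule (Section 6) puts the 3-month visit, when fixator removal is decided (Section 5.7), at day 91. Patients operated on in about the first 118 − 91 = 27 days had therefore reached that visit before the entry. The others had at most their 2-week and 6-week visits under the old form. The 6-month visit is at day 182, after day 118, so every affected patient still had the 6-month and 1-year visits to come.

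**The plan's own figures.** The count of 40 cannot be derived from anything else in the document. The pilot rate can: "Twelve patients (46.2%) treated with external fixators developed superficial infection" (Section 2.3), and 12/26 = 46.2%.

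**Inputs for the illustration.**
- True external-fixation rate p = 46.2% (pilot; an assumption for this trial).
- External-fixation patients N = 240/2 = 120 (Section 4.2, equal allocation); with the 192 expected in the final analysis, N = 96.
- Affected external-fixation patients k = 20 if the 40 are both arms together, or 40 if all are external fixation. The entry does not say which. At the planned pace, 240 × 118/365 ≈ 78 patients, about 39 of them external fixation, so the second reading cannot be ruled out. Actual enrolment is not given.
- Share of their infections missed m = 25%, 50%, 75% (assumed; the document gives no figure).

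**If missed infections are counted as absent**, the observed rate is p × (1 − m × k/N), and the shortfall is p × m × k/N.

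| N | k | m = 25% | m = 50% | m = 75% |
|---|---|---|---|---|
| 120 | 20 | 1.9 points | 3.8 | 5.8 |
| 96 | 20 | 2.4 | 4.8 | 7.2 |
| 120 | 40 | 3.8 | 7.7 | 11.5 |
| 96 | 40 | 4.8 | 9.6 | 14.4 |

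For example, N = 120, k = 20, m = 75%: 46.2 × 0.75 × 20/120 = 5.8 points, so the rate reads 40.4%.

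**If only the hidden-question cases are dropped**, the error changes sign, because the early patients who remain are those with a reported infection. With N = 120 and m = 50%:
- k = 20: (100 × 0.462 + 4.62)/(100 + 4.62) = 48.6%, which is 2.4 points too high.
- k = 40: (80 × 0.462 + 9.24)/(80 + 9.24) = 51.8%, which is 5.6 points too high.

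**If the whole early group is set aside**, neither error arises, provided early and later patients are alike. The cost is precision. The 95% half-width, 1.96 × √(p(1 − p)/n), goes from 8.9 points (n = 120) to 9.8 (n = 100), or from 10.0 (n = 96) to 11.2 (n = 76).

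**The case against.** The strongest reply has four parts.

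1. *Coding of unanswered items belongs in a statistical analysis plan, which is not shown.* This is right as far as it goes, and a missing coding rule alone would be no finding. But this document itself judges the loss to be minor and orders no recovery, and an analysis plan cannot restore answers that were never collected.

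2. *A reader might infer that hidden questions are recorded as no infection.* The documents do not say so. A field that was never displayed has no answer, and no rule converts blanks. The downward figures above are what would follow from that treatment, not a description of a stated procedure.

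3. *A reader might infer that the missed patients are the typical pin-tract cases, or that nearly all early infections were lost.* Neither is supported. The document gives no split of pin-tract infections by presence of a wound infection. The entry says that some early patients had wound infections and did see the question, so a complete miss contradicts the text. The pilot's 46.2% also covers all superficial infection, and part of that was reportable under the wound question throughout.

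4. *Later visits will catch some cases, and records may not show pin-site status.* Both are fair. Many early patients were still in a fixator at the change, which reduces the loss. Recall cannot reproduce the graded examination finding in Section 6.5, which limits what a look-back can recover.

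What stands is that infections already resolved at the change are lost unless someone looks for them.

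**Conclusion.** The point holds for a secondary outcome. The document concedes under-ascertainment in one arm, calls it slight without an estimate, and repairs the form in a way that cannot reach infections already resolved. Unless the early data are recovered or set aside, the external-fixation superficial infection rate is understated in the comparison with nailing.

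The illustrative size is about 2 to 6 percentage points. This assumes the pilot rate, 120 external-fixation patients, 20 of them affected, and 25% to 75% of their infections missed and counted as absent. It is larger if all 40 were external-fixation patients and smaller if later visits pick up some cases. The true rate and the share missed are assumptions.

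The primary outcome is essentially unaffected, because Section 4.1 keeps bedside treatment of superficial pin-site infection out of it. The gap is disclosed and closed for later patients, so this is a correction worth making and not a threat to the trial's main conclusion.

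**What to change.** 1. Replace the sentence that plays down the effect with a look-back covering every external-fixation patient who had a visit before the form change. Use the existing records, which are to be kept until the study ends (on-duty instructions following Section 5.10). Add one question at the next visit on any pin-tract infection since surgery. Mark these answers as retrospective. The same log shows that this is workable: on February 3 the team undertook to contact patients already seen about the cohort change, and noted a borderline patient for possible exclusion.
2. Treat pin-tract status at all visits before the change as not systematically assessed, and never as no infection. Do not drop only the visits where the question was hidden, because that keeps early patients selected on infection.
3. Report the superficial infection comparison with and without the whole group of early patients, taking both arms over the same enrolment period so that the randomised comparison is preserved.
4. State whether the 40 are all patients or external-fixation patients only.

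The cost is a review of at most 40 charts if that count is complete, one added question and one added analysis. The downsides are some recall error in the recovered answers and, in the analysis without the early group, a half-width about 1 point wider if 20 external-fixation patients are set aside, or about 2 points wider if 40 are (8.9 to 10.9 with N = 120).

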2.1 Significance: Extremity Trauma as Global Epidemic

More than 75% of the global population lives in low and middle-income countries (LMICs) where rates of extremity injury average 2-5 times higher than high-income countries (HICs).¹ Higher mortality rates in LMICs have been directly linked to the expanding use of motorized transport within the context of underdeveloped trauma care systems.² As evidence of this growing epidemic, road traffic crashes are predicted to become the eighth leading cause of death and the fourth leading cause of disability worldwide by 2030.³

The World Health Organization (WHO) projects Africa's road trauma burden, currently the highest in the world (19.1-28.3/100,000), to increase by 80% between 2000 and 2020.⁴ On this continent better known for its battle with HIV, tuberculosis, and malaria, injuries account for more deaths among children ages 5-14 than all three infectious diseases combined.⁵

To shape the focus of our proposed study, we focused our efforts where the clinical need is greatest. Epidemiologic data indicate that open tibia and fibula fractures constitute the most common open long bone fracture encountered in orthopedic practice, and most often result from road traffic accidents.⁶ This data is consistent with the MOI experience, where 96.2% of patients enrolled in our pilot study suffered open tibia fractures resulting from motorcycle or motor vehicle accidents.

Tibia fractures constitute severe, potentially limb-threatening injuries. Sixteen percent of patients in our preliminary study sustained associated injuries (18.5% musculoskeletal, 9.3% Traumatic Brain Injury). This is consistent with prior research documenting the prevalence of multiple open fractures at 6.4%, an average injury severity score of 14 (Range 1-75), and more severe fractures associated with motorcycle accidents.⁷ Authors of the landmark Lower Extremity Assessment Project (LEAP) study which prospectively followed outcomes of patients with severe open diaphyseal tibia fractures found that nearly 33% of patients with Gustilo and Anderson Type 3 injuries available at 2 year follow-up underwent early amputation due to initial injury severity.⁸

Patients with open tibia fractures also suffer from high complication rates, as the bone's precarious blood supply and relative lack of soft-tissue coverage compromise the healing process. The LEAP authors reported high rates of infection (11% to 38%), nonunion (7% to 60%), and secondary operative procedures.⁸ In their seminal 1984 paper, Gustilo and Anderson demonstrated the correlation of infection rates with increasing severity of injury by roughly an order of magnitude, as measured by their eponymous classification.⁹ This finding was confirmed by Papakostidis et. al., in a systematic review of 30,260 open tibial shaft fractures published in 2011.¹⁰ Tibia fracture complications lead to high rates of functional disability due to the importance of the tibia to lower extremity alignment, stability, and strength.

Adding demographic insult to injury, road traffic accidents resulting in severe open tibia fractures predominantly impact young men. Patients in our preliminary study were largely male (77.8%) and averaged 34 years of age. Thus, these injuries disable the most economically productive demographic in developing economies. Lost income over the average 6-8 month time required for return to work has a devastating impact on home finances. The economic implications of these injuries cascade through communities generating cycles of debt, poverty, and family hardship. Additionally, these high acuity patients require vast curative resources, overburdening an already under-resourced health system.

2.2 Innovation: Advancing Evidence Based Fixation of Severe Open Tibia Fractures

The optimal method of surgical fixation for severe tibial shaft fractures continues to be a popular topic in the orthopaedic literature. Despite thirty years of global research comparing external fixation to intramedullary nailing, controversy on the subject persists. Of the more than ten comparative studies published in the literature, most utilized retrospective, non-randomized research designs. Authors of previous meta-analyses note widespread bias toward external fixation with increased fracture severity, despite good evidence supporting both fixation methods for Gustilo 3A (and even 3B) fractures. This bias further highlights the need for prospective, randomized treatment group allocation. Additionally, authors of the most comprehensive systematic reviews note that high rates of allocation group heterogeneity confound comparison of results across studies. To date, there has been no randomized, prospective, adequately powered trial evaluating external fixation versus undreamed intramedullary nailing and no comparative trial of external fixation with reamed nailing technique.^{11, 12}

Proponents of external fixators argue that these devices can be applied rapidly with relative ease without radiographic guidance, and entail limited insult to already traumatized soft tissues. A major additional advantage in Sub-Saharan Africa is their relative low cost, particularly considering bars and clamps are often cleaned and re-used. While union rates in large series were reported at 94%, difficulty of closed reduction raises potential for higher rates of malunion, reported at 20% and 33% in meta-analyses by Bhandari and Giannoudis, respectively.^{11, 13}

Intramedullary nails offer a similar union rate of 95% with the advantages of controlling segmental fractures (thus limiting malunion rates to approximately 10%), preserving joint motion, and permitting early weight bearing in polytrauma patients. Relative disadvantages include longer operative time, higher implant costs, higher rates of implant failure (12.4% vs 2.4% for external fixation), and prevalence of post-operative anterior knee pain. Rates of delayed union are somewhat equivocal between techniques, reported at 24% for external fixation and 22% for intramedullary nailing. Deep infection rates for both techniques are highly variable, with reported rates for external fixation ranging from 5.7 to 16.2% while rates for intramedullary nailing range from 2.4% to 7%.^{10, 11}

When treating severe open tibial shaft fractures, most surgeons in HICs now employ a “damage control” approach which draws from the relative merits of both methodologies. This strategy involves the application of an external fixator to the traumatized limb during the initial phase of care, followed by planned conversion to intramedullary nailing after the patient has been fully resuscitated and the wound thoroughly debrided.

Orthopaedic surgeons at MOI, and across Sub-Saharan Africa, are generally familiar with using both external fixation and intramedullary nailing techniques. However, there is little, if any, empiric evidence to guide the choice of treatment. Often, the operative plan hinges not on the surgeon’s experience or clinical judgment, but on the cost and availability of surgical implants. Economic scarcity necessitates careful resource allocation. Surgeons must often utilize external fixation for definitive care, rather than converting all patients initially managed with external fixators to intramedullary nails. The impact of other clinical factors, such as patient comorbidities, operative timing, availability of antibiotics, and surgeon competence remain unknown.

Despite the high prevalence of injury and disability throughout Sub-Saharan Africa, Africans rarely benefit from peer-reviewed research. In a recent review of articles published in four leading orthopaedic journals over three years, publications from Sub-Saharan Africa accounted for only 0.4% of the 3964 articles reviewed and 5.6% of the 265 articles with developing world authorship.¹⁴ OREF has already begun the work of reversing this trend. This study proposal aims to build on the success of a collaborative research partnership made possible by previous OREF funding which examined plating versus intramedullary nailing of femoral shaft fractures.

We propose to undertake a randomized, prospective trial which will generate Level 1 evidence concerning optimal fixation methods for the treatment of severe tibia fractures in Dar es Salaam, Tanzania. Clinical and functional outcomes data obtained from our study will inform practice patterns of surgeons throughout Africa, helping to reduce patient morbidity, limiting the economic impact of injury, and minimizing health system expenditures by preventing complications which

would necessitate reoperation. Results would prove useful to orthopaedic surgeons worldwide, who would have the highest caliber scientific evidence with which to advocate for funding needed from policy-makers and charitable donors to address the growing epidemic of global extremity trauma. Perhaps more importantly, we hope to break the widely held perception that austere environments present unsurmountable challenges to meaningful clinical inquiry.

